1.1.2 Exploratory Prediction of KAM and Optimal Modification Direction

First, bivariate Pearson correlation coefficients will be calculated for the relationship between each clinical measure and each KAM outcome. Next, a mixed stepwise linear regression will be performed for each KAM outcome (early stance peak, late stance peak, and impulse). An alpha threshold for retaining and removing the predictor will be set to 0.05 and 0.10, respectively. Significant predictors will be entered into sequential multiple linear regression models for determining the amount of KAM outcome variance explained by the individual predictors. Possible predictors will include body mass, tibial alignment, walking speed, categorical FPA and continuous FPA. We will then use logistic regression analyses to predict the optimal direction of FPA modification, defined as the FPA direction (toe-in or toe-out) which produced the largest reduction in KAM impulse at 10° of change from natural FPA, as measured during the screening test.

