The above approach for screening can determine which modification is more optimal, resulting in improved biomechanical outcomes [35, 49]. However, this method of gait analysis is not feasible in clinical settings. Therefore, we will collect a series of measurements related to knee joint loading (specifically the KAM) that are clinically-available with the goal of examining their ability to predict whether a participant will reduce their KAM magnitudes more using toe-in or toe-out modification. These measures will include body mass (kg), frontal plane tibial angle (degrees), and walking speed (m/s), which will be collected using a standard bathroom scale, gravity inclinometer, and timing gates, respectively [50]. These measures alone predicted 67% of the variance in overall peak KAM (body mass = 41% alone) [50], which is often the early stance peak. In addition, FPA will be measured using both a categorical and continuous method. While wearing wet socks, participants will walk over a 3m long piece of medical exam table paper taped to the floor. First, FPA will be visually categorized as neutral, small toe-in/out, large toe-in/out by [name]. Then, the foot imprint made by the wet socks will also be measured to extract the angle between the long axis of the foot imprint and the walking direction. These data will be compared with the quantitative gait screening assessment outlined above to A) predict KAM magnitudes and B) predict the direction of FPA change that would result in the largest reduction in KAM magnitudes. This examination is exploratory, with the goal of informing future clinical trials in settings without access to motion capture.

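### SAP 1.1.2 puts two readings of the same foot angle into one stepwise model, so which of them is credited with explained KAM variance is partly chance

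*SAP*

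**What the plan says.** Protocol 4.3.1 A states that "FPA will be measured using both a categorical and continuous method". For the first method, "FPA will be visually categorized as neutral, small toe-in/out, large toe-in/out". For the second, the angle is taken from the wet-sock imprint on paper. No numeric score is given for the categories, and the slash wording leaves open whether direction is kept (five ordered levels) or dropped (three).

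SAP 1.1.2 has three steps for KAM magnitude.

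- First, "bivariate Pearson correlation coefficients will be calculated for the relationship between each clinical measure and each KAM outcome", with no exception for the category.
- A mixed stepwise regression is run for each of three outcomes: early stance peak, late stance peak and impulse. On thresholds, "An alpha threshold for retaining and removing the predictor will be set to 0.05 and 0.10, respectively". On candidates, "Possible predictors will include body mass, tibial alignment, walking speed, categorical FPA and continuous FPA".
- Then, "Significant predictors will be entered into sequential multiple linear regression models for determining the amount of KAM outcome variance explained by the individual predictors".

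Neither document lets only one FPA reading enter a model, and neither plans a collinearity or stability check. Protocol 4.3.1 A calls the work exploratory and intends it to inform trials without motion capture.

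**The concern.** The category and the imprint angle are two noisy readings of one quantity. Once one is in a stepwise model, the other has little left to explain and will usually fail the entry test. Which enters first depends on which has the smaller p-value in that sample. With two closely correlated candidates and a small sample, the less precise one will sometimes win.

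The sequential model then assigns the FPA-related variance to the winner, and the other reading looks uninformative. A later trial team could choose between the quick visual rating and the imprint on the strength of that result.

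A smaller gap lies in the bivariate step. A correlation with a category depends on the score given to it. Protocol 2.3 describes toe-in and toe-out as acting on different parts of stance, so a score that ignores direction could hide an association.

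**Working it through.** SAP 1.1.2 states no figure, so there is none to reproduce. The protocol's minimum of 14 participants belongs to the primary analysis of covariance and does not bear on this point.

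**Inputs from the documents**
- Five candidates: body mass, tibial alignment, walking speed, categorical FPA, continuous FPA (SAP 1.1.2).
- Thresholds 0.05 and 0.10 (SAP 1.1.2), read as p < 0.05 to enter and p > 0.10 to remove.
- Body mass explains 41% of overall peak KAM variance; mass, tibial angle and speed together explain 67% (Protocol 4.3.1 A). The remaining 67 − 41 = 26% is split evenly, 13% each.
- 30 participants enrolled (Protocol 4.2.2). The number screened, and so the N for SAP 1.1.2, is not stated. N = 30 and N = 60 were tried.

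**Assumptions, not in the documents**
- True FPA has mean 7° and SD 6°.
- Imprint error SD is 1.7°; visual-rating error SD is 1.7°, 3° or 5°.
- Category cut-points are −10°, −3°, 3° and 10°, scored −2 to +2.
- The FPA effect is ρ = 0.2 or 0.3 SD of KAM per SD of FPA.

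**Model**

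KAM = √0.41·mass + √0.13·tibial + √0.13·speed − ρ·z(FPA) + √(1 − 0.67 − ρ²)·noise

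The residual variance is 0.33 − 0.04 = 0.29 for ρ = 0.2, and 0.33 − 0.09 = 0.24 for ρ = 0.3. Forward-backward selection was run 600 times per setting.

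**Results at N = 30.** The last column is category only ÷ (1 − neither).

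| ρ | Visual error SD | r between readings | Imprint only | Category only | Both | Neither | Category share |
|---|---|---|---|---|---|---|---|
| 0.2 | 1.7° | 0.85 | 0.273 | 0.148 | 0.010 | 0.568 | 0.148/0.432 = 34% |
| 0.2 | 3° | 0.79 | 0.270 | 0.152 | 0.012 | 0.567 | 0.152/0.433 = 35% |
| 0.2 | 5° | 0.68 | 0.320 | 0.108 | 0.002 | 0.570 | 0.108/0.430 = 25% |
| 0.3 | 1.7° | 0.85 | 0.507 | 0.317 | 0.013 | 0.163 | 0.317/0.837 = 38% |
| 0.3 | 3° | 0.79 | 0.602 | 0.183 | 0.005 | 0.210 | 0.183/0.790 = 23% |
| 0.3 | 5° | 0.68 | 0.625 | 0.130 | 0.020 | 0.225 | 0.130/0.775 = 17% |

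Simulation error on a share is about 3 percentage points: in the first row, √(0.343 × 0.657/259) = 0.03, where 259 = 600 × 0.432.

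At N = 60 the share runs from 0.08/0.99 = 8% to 0.27/0.802 = 34%, and both readings are kept in at most 2.3% of runs. A separate run with all five candidates, again under assumed spread, error and cut-points, gave shares of 21-46% and both readings in 0-3%. With no FPA effect at N = 30, an FPA term still entered in about 9% of runs, split almost evenly (4.7% imprint only, 4.2% category only).

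**Coding of the category in the bivariate step.** With a true correlation of −0.30, the same cut-points and no rating error:

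| Score | Mean FPA 7° | Mean FPA 0° |
|---|---|---|
| Signed, five levels | −0.28 | −0.28 |
| Unsigned, three levels | −0.24 | 0.00 |

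**How the two readings can be compared fairly.** Entered as an unordered factor, the five-level category uses up to 4 degrees of freedom against 1 for the angle. On raw R-squared the factor beat the imprint in 38-75% of simulated samples; a signed one-degree-of-freedom score beat it in 21-46%.

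**The case against.** The plan's first step already gives each reading its own unadjusted coefficient against the same three outcomes. A reader might infer that the plan cannot compare the two readings at all; the documents do not support that. Nor do they ask whether the visual rating can replace the imprint. The two aims in Protocol 4.3.1 A are to predict KAM magnitude and to predict the better direction of change. For pure prediction, dropping one of two redundant readings is what stepwise selection is meant to do. All of this stands and limits the point to the attribution of variance.

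A reader might also infer that Pearson on the category is invalid. It is not: the categories are ordered, direction is central throughout the protocol, and a signed integer score loses little. What is missing is one line on coding.

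Nor is the selection a coin toss. The imprint alone was kept more often than the category alone in every setting with a real FPA effect, and neither reading survived in 16-57% of runs at N = 30. The percentages rest on assumed spread, rater error and cut-points. What the objection does not remove is that SAP 1.1.2 goes on to credit variance to individual predictors, and nothing in it stops the coarser reading from taking that credit by chance.

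**Conclusion.** The point holds as a minor one. With both FPA readings as candidates, the stepwise model almost never keeps both (about 0-3%). In samples near the enrolled size that keep an FPA term, the coarser category is the sole survivor in roughly 20-45%; the tabulated runs gave 17-38% and the separate run 21-46%. A larger screened sample reduces this but does not remove it: 8-34% at N = 60. The variance credited to a particular FPA reading should therefore not be taken as evidence that it is the better measure.

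The exact percentages depend on the assumptions listed, but the instability appeared across the whole range tried. No primary or secondary outcome, eligibility decision or assigned direction of modification is affected. The logistic regression for direction is outside this point, since these simulations do not cover it.

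**What to change.** Amend SAP 1.1.2 along these lines:

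> For each KAM outcome, two models will be fitted with the same other predictors (body mass, tibial alignment, walking speed): one with continuous FPA, and one with the visual category as a signed ordered score from large toe-in to large toe-out, using one degree of freedom. The two readings will not enter the same model. Adjusted or optimism-corrected (bootstrap or cross-validated) R-squared will be reported for each model with its interval. The comparison is exploratory. The same signed score will be used in the bivariate step, with either Pearson or Spearman applied to all measures.

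The direction seen must be recorded with each visual category. The category should not be entered as an unordered factor and compared on raw R-squared, because its extra degrees of freedom favour it.

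The text should also say that the sample is unlikely to separate the two readings. In a simulation at N = 35 with the category as a factor and no other predictors, the bootstrap 95% interval for the R-squared difference had a median width of 0.35-0.43 and covered zero in 87-96% of samples.

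The cost is a few lines of SAP wording and one extra model per KAM outcome, three in all. No new measurement is needed if direction is recorded.

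### The KAM prediction models are selected and scored on the same small sample, so their reported R² will overstate performance in new people, and no correction is planned

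*SAP*

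**What the plan says.** SAP section 1.1.2 begins with Pearson correlations between each clinical measure and each KAM outcome. Then "a mixed stepwise linear regression will be performed for each KAM outcome"; there are three outcomes (early stance peak, late stance peak, impulse). The thresholds are given as "An alpha threshold for retaining and removing the predictor will be set to 0.05 and 0.10, respectively", read here as entry at 0.05 and removal at 0.10. The candidates are listed: "Possible predictors will include body mass, tibial alignment, walking speed, categorical FPA and continuous FPA". After selection, "Significant predictors will be entered into sequential multiple linear regression models for determining the amount of KAM outcome variance explained by the individual predictors". A logistic regression for the better direction, toe-in or toe-out, follows. The SAP gives it no selection step, no predictor list of its own and no accuracy measure.

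Protocol section 4.3.1 A calls the examination exploratory and gives its purpose as "with the goal of informing future clinical trials in settings without access to motion capture". It also says that "FPA will be visually categorized as neutral, small toe-in/out, large toe-in/out", which could mean up to five levels; the coding is not given.

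Neither document mentions a hold-out set, cross-validation, bootstrap, shrinkage, adjusted R² or any other correction for optimism. Neither gives a sample size for this analysis. Protocol section 4.2.2 plans 30 participants for the trial.

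**The concern.** Choosing predictors by p-value favours those whose association happens to be large in the sample at hand. Estimating their explained variance on that sample then counts the same chance variation again. The resulting R² describes fit to these participants, not prediction for others. A later trial that replaces motion capture with a scale, an inclinometer, timing gates and a wet footprint needs the second quantity, and the plan does not estimate it.

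The direction model has a related problem with a different cause. A logistic model with several parameters and few participants in the smaller direction group will separate its own fitting data better than new data, with or without a selection step. What is at stake is how much confidence future investigators place in the clinical measures. No decision within this trial is involved.

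**Working it through.** **Figures in the plan.** There is none to reproduce for this analysis. The minimum of 14 in protocol section 4.2.2 belongs to the primary analysis of covariance and is not an input here. The protocol does cite 67% of variance in overall peak KAM explained by mass, tibial angle and speed (mass alone 41%), and this serves as the strong-signal scenario.

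**Inputs from the documents.** Five candidate predictors; entry 0.05, removal 0.10; refit on the selected set; 30 recruited.

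**Assumptions.** Analysed n of 30, with 60 as an alternative if everyone screened is used; correlation of 0.8 between the two foot progression angle measures; true R² of 0, 0.20, 0.40 or 0.67.

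**Stepwise KAM models.** Each simulated data set went through the stepwise procedure and refit. The fitted model was then scored in 4,000 new subjects. Optimism = apparent R² − new-data R².

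| n | True R² | Apparent | New data | Optimism |
|---|---|---|---|---|
| 30 | 0 | 0.04 | −0.08 | 0.12 |
| 30 | 0.20 | 0.19 | −0.02 | 0.21 |
| 30 | 0.40 | 0.40 | 0.19 | 0.21 |
| 30 | 0.67 | 0.67 | 0.57 | 0.10 |
| 60 | 0 | 0.02 | −0.04 | 0.06 |
| 60 | 0.20 | 0.21 | 0.08 | 0.13 |
| 60 | 0.40 | 0.41 | 0.32 | 0.09 |
| 60 | 0.67 | 0.68 | 0.64 | 0.04 |

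A negative value means the model predicts worse than the mean. Repeat runs at n=30 and true R² 0.40 gave 0.38 versus 0.16, hence the ranges quoted.

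With no signal at n=30, at least one predictor is kept in 20% of runs per outcome, with mean apparent R² of 0.20 in those runs. Over all runs this is 0.20 × 0.20 = 0.04; a smaller set of runs gave 0.05.

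**Shares of individual predictors, n=30.** A secondary predictor with a share of 0.13 when total R² is 0.67 has a share of 0.13 × 0.40/0.67 = 0.08 when total R² is 0.40. When selected, its mean apparent share is 0.15 in the first case and 0.17 in the second.

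**Direction model, no selection step.** At n=30 with a 15/15 split, events per parameter are 15/5 = 3.0. If categorical foot progression angle takes four indicator terms, they are 15/8 = 1.9. With no signal (true AUC 0.50):

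- n=30: apparent AUC 0.73 with five parameters, 0.80 with eight.
- n=60: 0.65-0.67 with five, 0.71 with eight.

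With one real predictor (assumed log-odds 0.8 per SD) at n=30, apparent AUC is 0.80-0.84 against 0.60-0.63 in new data.

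**Does a correction work?** Corrected R² = apparent R² − mean over resamples of (R² of the resample's model in its own resample − R² of that model in the full sample), with stepwise selection repeated each time. At n=30:

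| True R² | Apparent | Corrected | Actual new data |
|---|---|---|---|
| 0 | 0.05 | −0.14 | −0.10 |
| 0.40 | 0.38 | 0.19 | 0.19 |
| 0.67 | 0.69 | 0.57 | 0.57 |

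The correction recovers new-data performance closely where there is signal and is slightly too severe where there is none.

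**The case against.** The best defence is that the analysis is labelled exploratory, decides nothing in the trial, and rests on predictors with a known strong signal. Much of this stands. Each participant's direction comes from their own measured gait-screen response (protocol sections 4.3.1 B and 4.3.5), and no clinical rule or cut-off is promised. The analysed set may also exceed 30, because the measures are taken at screening, before non-responders are excluded and before the X-ray. The label does not remove the optimism, however, and the stated purpose is use in other settings.

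Three stronger readings are tempting and not supported.

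- A reader might infer that the reported R² will be mostly noise. That holds for null or weak signals. At the cited 67%, mean apparent R² is close to the population value and the loss in new people is about 0.10. That citation covers overall peak KAM only, so it does not settle late stance peak, impulse or direction.
- A reader might infer that stepwise selection inflates the direction model. The SAP plans stepwise selection only for the linear KAM models; the direction model's optimism comes from scoring it on its own fitting data.
- A reader might infer that the plan promises an AUC or accuracy figure. It names neither, so the AUC results apply only if such a figure is reported.

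**Conclusion.** The point holds as a low-priority improvement. As planned, R² for the stepwise KAM models will on average exceed new-person performance by roughly 0.10-0.21 at n=30 and 0.04-0.13 at n=60, and the shares credited to weaker selected predictors will be too large. Any AUC computed on the direction model's own data would also be optimistic. The sizes depend on the assumed analysed number, signal strength, predictor correlation and direction split, none of which the documents fix for this analysis. The direction of the bias does not change across the ranges examined.

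**What to change.** Add to SAP section 1.1.2, in substance:

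- The full procedure (stepwise selection and refit) will be repeated in bootstrap resamples, for example 500, and the optimism-corrected R² will be reported beside the apparent R² for each KAM outcome.
- If discrimination of the direction model is reported, an optimism-corrected AUC from the same bootstrap will accompany it, using a penalised (e.g. Firth) logistic fit throughout.
- The analysed set will be named: everyone screened, or enrolled participants only.

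The penalised fit is needed because ordinary logistic regression has no finite estimate under complete separation. In simulation at n=30 with five predictors, separation occurred in about 5-11% of resamples with a 15/15 split and 25-34% with 6/24.

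The cost is a little more code and lower reported figures. No new data or visits are needed, and the feasibility and efficacy analyses stay as they are.

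### SAP 1.1.2 reads individual predictors' shares of KAM variance from sequential regression without stating an entry order, on which the shares depend when predictors are correlated

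*SAP*

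**What the plan says.** SAP 1.1.2 sets out three steps for the KAM outcomes before it turns to direction of modification.

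- Simple correlations: "First, bivariate Pearson correlation coefficients will be calculated for the relationship between each clinical measure and each KAM outcome".
- Selection by mixed stepwise regression, run separately for the early stance peak, the late stance peak and the impulse: "An alpha threshold for retaining and removing the predictor will be set to 0.05 and 0.10, respectively".
- Attribution of variance: "Significant predictors will be entered into sequential multiple linear regression models for determining the amount of KAM outcome variance explained by the individual predictors".

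The candidates are named: "Possible predictors will include body mass, tibial alignment, walking speed, categorical FPA and continuous FPA". A logistic regression for the better FPA direction follows.

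Protocol 4.3.1 A) describes the measurements. Of FPA it says: "In addition, FPA will be measured using both a categorical and continuous method". Both come from the same wet-sock walk, one as a visual category and one as an angle taken from the imprint. The same section cites an earlier result for body mass, tibial angle and walking speed: "These measures alone predicted 67% of the variance in overall peak KAM (body mass = 41% alone". It also gives the status of the work: "This examination is exploratory, with the goal of informing future clinical trials in settings without access to motion capture".

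Neither document states the order in which predictors enter the sequential models or says that the stepwise order carries over. Neither plans a within-model share that is free of order.

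**The concern.** A sequential R2 step measures what a predictor adds to those already in the model. Variance that correlated predictors share is credited to whichever enters first. The step equals a predictor's own contribution in every order only when the predictors are uncorrelated, and a larger sample does not change this.

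The SAP's stated purpose is the variance explained by individual predictors. With no order fixed, two analysts could follow the text faithfully and report different shares from the same data. If the stepwise order is used, the measure picked first in this sample takes all the variance that it shares with the rest.

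What is at stake is how a later team, planning a trial without motion capture, reads the relative value of the simple clinical measures.

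**Working it through.** The documents give no figure for this analysis that can be reproduced. The 67% and 41% are results of a cited study and serve only as inputs to an illustration.

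**Inputs from the protocol (4.3.1 A)**
- Body mass alone: r1² = 0.41, so r1 = 0.640.
- Body mass, tibial angle and walking speed together: R2 = 0.67. This is for overall peak KAM.

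**Assumed, because the documents do not give them**
- The correlation c between body mass and a single composite of the other predictors.
- The correlations of the two FPA measures with each other and with KAM.

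**1. Body mass against a composite of the rest.** For two predictors,

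R2 = (r1² + r2² − 2·r1·r2·c) / (1 − c²).

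Set R2 = 0.67 and r1² = 0.41, and solve for r2 (positive root):

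r2² − 2·r1·c·r2 + 0.41 − 0.67(1 − c²) = 0.

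Entered first, body mass gets 0.41 and the composite gets 0.67 − 0.41 = 0.26. Entered last, body mass gets 0.67 − r2² and the composite, now first, gets r2².

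Example, c = 0.3: r2² − 0.384·r2 − 0.1997 = 0, so r2 = 0.679 and r2² = 0.46. Body mass entered last gets 0.67 − 0.46 = 0.21.

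| Assumed c | r2 | Body mass first | Body mass last | Composite first | Composite last |
|---|---|---|---|---|---|
| −0.3 | 0.294 | 0.41 | 0.58 | 0.09 | 0.26 |
| 0 | 0.510 | 0.41 | 0.41 | 0.26 | 0.26 |
| 0.1 | 0.571 | 0.41 | 0.34 | 0.33 | 0.26 |
| 0.3 | 0.679 | 0.41 | 0.21 | 0.46 | 0.26 |
| 0.5 | 0.762 | 0.41 | 0.09 | 0.58 | 0.26 |

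The total is 0.67 in every row and either order. At c = 0 order makes no difference. At negative c, body mass gains by entering last.

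**2. The two FPA measures.** Suppose each correlates 0.4 with KAM and they correlate ρ with each other. Together R2 = 2(0.4²)/(1 + ρ). Whichever enters first gets 0.4² = 0.16, and the other gets R2 − 0.16:

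- ρ = 0.5: 0.213 − 0.16 = 0.053
- ρ = 0.7: 0.188 − 0.16 = 0.028
- ρ = 0.8: 0.178 − 0.16 = 0.018
- ρ = 0.9: 0.168 − 0.16 = 0.008

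This arises only if both survive selection.

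**3. Chance correlation in a small sample.** A simulation used three predictors, a population R2 of 0.67, n = 30, 500 samples and no selection step. It recorded the spread of body mass's share over all entry orders. The median spread was 0.11, 0.20 and 0.32 for true correlations among the predictors of 0, 0.2 and 0.4. So shares move with order at this size even when the predictors are truly uncorrelated. The 30 is the trial's recruitment target. The number analysed from the screening visit is not stated.

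**The case against.** The strongest reply is that an incremental R2 is a conventional and well-defined quantity once its order is given. The preceding stepwise run offers a natural order, and in a large sample that order would usually settle. This stands. A reader might infer that the reported importance of body mass, alignment, speed and FPA would be arbitrary, but the documents do not support that. The gap is an unstated order together with an interpretation that the steps alone cannot carry.

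A reader might also infer from the table that the ranking of the clinical measures reverses. It does not show this. The rival to body mass is a composite of several predictors, not a measure anyone would report. Even against the composite, reversal needs c above about 0.11. At 0.1 body mass leads either way (0.41 against 0.26, 0.34 against 0.33), and likewise at −0.3. Every value of c is assumed.

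Three further points stand:

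- The planned Pearson correlations, once squared, give each measure's stand-alone share regardless of order. A useful measure would therefore not be hidden by its place in the sequence. What they do not show is what a measure adds to the others.
- Only significant predictors enter the sequential models. Stepwise selection will often drop one of two overlapping FPA measures, which limits the worst case.
- The protocol's stated aims for this work are to predict KAM and the better direction. Entry order affects neither.

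The reply does not remove the core point. The SAP does not say that the stepwise order is used, and it assigns the sequential step the task of measuring individual contributions.

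**Conclusion.** The point holds as a low-priority improvement. SAP 1.1.2 uses sequential R2 steps to describe individual predictors without fixing an order, and those steps depend on order whenever predictors are correlated.

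On the protocol's cited figures, body mass would get 41% entered first. Entered last, it would get between 9% and 58% over assumed correlations from 0.5 to −0.3. These sizes rest on assumed correlations, on treating the other predictors as one composite, and on results for overall peak KAM from a cited study. They show how far order can matter, not what this trial will find.

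Total R2, fitted KAM values, the Pearson correlations and the logistic model for direction are unaffected. The analysis is exploratory, and no primary or secondary outcome depends on it.

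**What to change.** In SAP 1.1.2:

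- State the entry order if the sequential steps are kept, for example the order of stepwise entry or a named clinical order.
- For each retained predictor, report the squared semi-partial correlation (the loss in R2 when it is removed from the final model) beside its sequential step and its squared Pearson correlation.
- Give total R2 once per KAM outcome.
- Do not present sequential steps alone as individual contributions.

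R2 averaged over all entry orders (LMG) is optional. If bootstrap intervals are added, each resample should repeat the stepwise selection. Resampling only the final model would ignore the uncertainty from selection.

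The change uses the same data and needs a revised SAP passage and a few lines of code. Its only downside is a slightly longer results table.
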